## 20. Safety

The number and percentage of patients experiencing specific complications at any time during the 28 days post baseline, will be reported for both groups. Complications to be summarised are those appearing on the Outcome CRF.

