### 6.1. EAMS Background

The MHRA EAMS (Early Access to Medicine Scheme) is a form of compassionate use programme. EAMS aims to give patients with life threatening or seriously debilitating conditions access to medicines that do not yet have a marketing authorisation when there is a clear unmet medical need. The scheme is voluntary and operates within the current regulatory structure. The MHRA requires that a Registry be utilised to support capture of the real-world outcomes of the use of an EAMS medicine in UK patients. Data captured through an EAMS are expected to be used to support cost effectiveness and commissioning discussions as the medicine is licensed and becomes available for routine clinical use in the UK.

The Deputy Chief Medical Officer (DCMO) for Her Majesty's Government has mandated that data on all patients that receive Remdesivir through the EAMS must be captured through the ISARIC 4C Clinical Characterisation Protocol UK (CCP-UK) case report forms (CRFs), as coordinated by the COVID-19 Clinical Information Network (CO-CIN). Completion of the mandatory fields of the ISARIC WHO CCP-UK CRFs is required, to support ongoing implementation, including determination of future drug allocations between NHS hospitals, and evaluation ([link to forms](#)).

The DCMO has commissioned an analysis of efficacy and safety based on the pragmatic data being collected by CO-CIN.

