#### 8.4. Patient population studied

Inclusion/exclusion guidelines for RDV use changed slightly over time. The following criteria are designed to create a cohort of patients that would have been eligible to receive RDV from baseline. They apply for the whole study period, and will be used to define our analysis cohort:

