##### 8.4.2. Exclusion criteria

- Requiring a high flow cannula, any ventilation or ECMO during first 24 hours post baselinec
- Pregnant
- Chronic kidney disease
- RDV initiated  $> 24$  hours post baselined
- Is a COVID-19 re-admission (was previously hospitalised for COVID-19)
- Missing Day 1 Daily Treatment CRF
- Missing ‘Medication’ section of the Outcome CRF

---

a RDV was recommended in people aged 12 and over, and weighing over 40kg. Weight was not generally measured at baseline for practical reasons, so we have excluded children aged 12-17 in order to be sure that no-one in the control group was likely to weigh less than 40kg.

b This criteria is an ideal, to measure the effectiveness of RDV initiated close to baseline. If RDV is more routinely given later than this, we will either remove this criteria, or move the window of inclusion to say 3 days. Statistics describing when RDV treatment was initiated compared with baseline, will be presented.

c This subgroup will be analysed separately (see Section 19).

d See footnote b above.

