### 8.7. Definition of treatment groups

The analysis cohort will be split into two treatment groups: RDV and non-RDV. As the study is observational, allocation of treatment is decided by clinicians.

A matching process will be carried out to link RDV patients with non-RDV patients as follows:

A logistic regression with dependent variable RDV (Yes/No) will be fitted including the following covariates:

1. Month of baseline
2. Tier of participating centre (0 / 1 and 2)
3. Sex
4. Age
5. Broad ethnicity group (White / Asian / Black / Other)
6. Clinically extremely vulnerable status (Yes: Cancer / Yes: Severe respiratory condition / Yes: on immunosuppression therapy / Yes: Other / No)
7. Comorbidities: Diabetes (Y/N), Hypertension (Y/N), Obesity (Y/N), Chronic Cardiac disease (Y/N), CPD (Y/N), Asthma (Y/N)
8. Where COVID was acquired (Community / Hospital)
9. Admitted to HDU/ICU at baseline (Y/N)

Note: a pragmatic approach will be taken – the list above defines a best-case set of matching criteria; it may be necessary for categories to be collapsed to simplified discriminators (e.g. White vs Other ethnicity, or ‘Total number of comorbidities’), should the model become over-parametrised. If possible, 2nd order interactions will be investigated, and if statistically significant, added to the model. All main effects will be retained in the model, even if not significant.

The fitted model will be used to calculate the probability of receiving RDV for each patient according to their baseline factors. The probability calculated is called their propensity score (PS). Boxplots will

be presented showing the distribution of PS in each treatment group. Patients who were given RDV will then be matched to a control patient / patients with a similar PS who did not get RDV, using a nearest neighbour matching algorithm and a pre-specified maximum difference in PS (calliper width) of 0.2 standard deviations. The ratio of RDV patients to controls may be 1:1 or higher – to a maximum of 1:4 (Rassen (2012) suggests that 1:n matching leads to higher precision in estimating effect sizes, with a cost of a small increase in bias with increasing n). Controls are chosen without replacement, so may not be matched to more than one RDV patient.

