## 15. Treatments received

This study did not define an *a priori* protocol for clinicians treating COVID-19 patients. Reporting of protocol deviations will be limited to a count of patients that did not receive RDV according to guidelines, and to an assessment of missingness in the derivation of the primary and secondary outcomes. Treatments received are recorded in the Medication section of the Outcome CRF. These will be summarised in the matched cohort, split by treatment group. If there is evidence of imbalance between groups with respect to certain treatments, we will consider whether to adjust for this in the final analysis.

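### Section 20 reports complications only within the efficacy cohort, so remdesivir recipients excluded for kidney disease, pregnancy or re-admission, and by default late starters, have no complication report

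*SAP*

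**What the plan says.** Section 20 is the SAP's only section on safety. It states: "The number and percentage of patients experiencing specific complications at any time during the 28 days post baseline, will be reported for both groups". The complications are those listed on the Outcome CRF. No separate safety population is named.

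The groups come from Section 8.7: "The analysis cohort will be split into two treatment groups: RDV and non-RDV". The cohort comes from the Section 8.4 criteria, of which the SAP says: "They apply for the whole study period, and will be used to define our analysis cohort". Section 8.4.2 lists, among other exclusions, "Chronic kidney disease", pregnancy, re-admission for COVID-19, and "RDV initiated $> 24$ hours post baseline". The timing exclusion can be relaxed. Footnote b, to which footnote d refers back, says: "If RDV is more routinely given later than this, we will either remove this criteria, or move the window of inclusion to say 3 days". No such provision is attached to the other three.

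On purpose, Section 6.1 says: "The DCMO has commissioned an analysis of efficacy and safety based on the pragmatic data being collected by CO-CIN". Section 13.1 gives the aim as evaluating the use of RDV so far.

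**The concern.** The Section 8.4 criteria are meant to form a cohort of patients who would have been eligible for RDV from baseline. That serves a fair comparison of treated and untreated patients. A description of what happened to people given the drug has no need of that restriction, but Section 20 inherits it because it names no population of its own.

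What is at stake is the completeness of the safety half of the commission. Acute renal injury or failure is a named secondary outcome (Section 17.2.2.9), while recipients with known chronic kidney disease are removed before it is counted. A pattern of complications confined to one of the excluded strata could not appear in the report, and a reader of the safety table would not see that these recipients are missing from it.

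**Working it through.** No formula applies and the SAP gives no figure to reproduce. The check traces the population definitions and then looks for any other section that reports on the excluded recipients.

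**Population chain**

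1. Section 20 reports on both groups.
2. Section 8.7 defines the groups as a split of the analysis cohort.
3. Section 8.4 defines that cohort by its inclusion and exclusion criteria.
4. A recipient excluded under 8.4.2 is therefore in neither group. Section 20 does not say whether it means the full analysis cohort or the matched cohort, but the result is the same on either reading.

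**Other places where these recipients might be covered**

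| Section | What it provides | Does it report complications for them? |
|---|---|---|
| 8.4, footnote b | Statistics on when RDV was started; possible relaxation of the 24-hour rule | Late starters only, and only if the rule is relaxed |
| 8.7 | Separate description of unmatched patients | No; unmatched patients are members of the cohort |
| 14 | Flow chart with numbers excluded | No; counts of patients only |
| 15 | Deviation reporting that covers RDV use only as "limited to a count of patients that did not receive RDV according to guidelines" | No; a count only |
| 19 | Repeat of the preceding analyses, including the renal and liver outcomes, in patients ventilated in the first 24 hours | No; a different excluded subgroup |

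**Which recipients are left without a report**

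- Chronic kidney disease, pregnancy, re-admission: omitted with no relaxation.
- Start after 24 hours: omitted by default. If the criterion is removed, all of them enter on this count. If the window moves to about 3 days, those starting later still remain outside.
- Recipients outside the cohort for other reasons, such as age 12 to 17: also omitted.

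Not all of this is use outside the guidelines. Section 8.2 describes RDV as recommended no later than 10 days from symptom onset, so a patient starting more than 24 hours after admission may be within guidelines and would then not enter the Section 15 count. Footnote a says RDV was recommended from age 12 and explains that ages 12 to 17 are left out to avoid low-weight controls, which is a reason of comparability.

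**Size**

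Section 10 expects more than 500 RDV patients, but that figure refers to patients who satisfy the inclusion criteria. It says nothing about how many recipients fall outside, and no other section does. The omitted number therefore cannot be calculated.

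**Time origin**

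Section 20 counts complications over the 28 days from baseline. Section 8.3 sets baseline at hospitalisation for community-acquired disease, or at collection of the positive test for hospital-acquired disease, and notes that RDV may begin later. For a patient starting RDV on day d after baseline, events in the first d days precede any dose, and at most 28 − d days of follow-up remain, because Section 8.8 stops at day 28. An all-recipients table that kept the baseline origin would mix events before and after the first dose.

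**The case against.** The strongest reply is one of scope. The objectives in Section 7 concern efficacy only, in newly diagnosed, non-ventilated patients. The commissioning sentence and the requirement to capture data on all recipients stand in the EAMS background, and EAMS status ended in July 2020. The wider protocol is not at hand, and nothing says that this SAP is the only vehicle for safety in every recipient. Section 20 is descriptive and promises no conclusion about all UK use. This stands as a reason to treat the point as an incompleteness and not as an error. It does not remove the point: Section 6.1 names safety as commissioned, Section 6.1.2 says the data collection continued after EAMS, and Section 13.1 states the aim as evaluating use so far.

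Several stronger readings are tempting, and the document does not support them:

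- *That late starters are necessarily omitted.* Footnote b would admit some or all of them if later starting proves routine, so their omission is the default and not a certainty.
- *That a large share of recipients is lost.* No such share is given. If most of a large share were late starters, that is the situation in which footnote b would come into play.
- *That every excluded or unmatched recipient is ignored.* Patients ventilated early have their own analysis in Section 19, including renal and liver outcomes, and unmatched patients are described separately.
- *That the excluded patients are the ones most likely to be harmed.* The SAP does not say so. Recipients with kidney disease or pregnancy may also be few, since the criteria aim at patients eligible for RDV.

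It is also fair to say that an uncontrolled table cannot separate acute renal injury due to RDV from that due to underlying kidney disease.

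**Conclusion.** The point holds as a gap in reporting. As written, complications in RDV recipients excluded for chronic kidney disease, pregnancy or re-admission are reported nowhere, and neither are those in recipients starting after 24 hours unless footnote b is invoked. The size of the omitted group is unknown. The conclusion rests only on the SAP's own definitions and on reading the Section 20 groups as those of Section 8.7, the only treatment groups that the SAP defines. It does not depend on how many recipients were excluded or on any view of their risk.

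This is not a contradiction in the plan, and the efficacy analyses stand. It is a worthwhile, inexpensive improvement, because it changes what the safety report is able to show.

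**What to change.** In Section 20:

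1. State whether the existing two-group summary uses the full analysis cohort or the matched cohort.
2. Add a descriptive table of Outcome CRF complications and deaths for every patient recorded as receiving at least one dose of RDV and having an Outcome CRF.
3. Give separate rows by reason for exclusion: chronic kidney disease, pregnancy, re-admission, start after 24 hours, and other.
4. For late starters, count events from the first RDV dose where dates allow. Otherwise flag that events may predate RDV.
5. Label the table as non-comparative, and keep the matched cohort for all comparative analyses.

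The cost is SAP wording, an entry in Change Control, and one or two further tables from data already collected. The drawbacks are small strata, no comparator, and some events whose timing relative to the first dose will remain uncertain.

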## 21. Declarations

The manufacturer of Remdesivir, Gilead, is also involved in funding other trials that the Liverpool Clinical Trials unit is co-ordinating: a randomised controlled trial (HART-CT) that is fully funded by Gilead and sponsored by the University of Liverpool; and a trial (REALTO) that is part funded by Gilead. [name] is the lead statistician on the HART-CT trial.

## Appendix

Table 1: Clinical status ordinal score at day 15 mapped to ISARIC data fields

Score	Clinical Status	ISARIC v9.3 Data Field(s)
1	Not hospitalised, and no limitations on activities	
OUTCOME CRF (if dated day 15 or less):
 
 
• Discharged alive expected to survive = YES
 
AND
 
• Ability to self-care at discharge = ‘Same as before illness’ OR ‘Better’
 
AND
 
• Oxygen therapy?* = NO
 
 
OR
 
 
• Hospitalisation= YES
 
AND
 
• Medically fit for discharge = YES
 

2	Not hospitalised, limitation on activities and/or requiring home oxygen	
OUTCOME CRF (if dated day 15 or less):
 
 
• Discharged alive expected to survive = YES
 
AND
 
• Ability to self-care at discharge = ‘Worse’
 
OR
 
• Oxygen therapy? = YES
 

3	Hospitalised, not requiring supplemental oxygen – no longer requiring ongoing COVID related medical care	
OUTCOME CRF (dated day 15 or less):
 
 
• Hospitalisation= YES
 
 
AND
 
 
• Ongoing health care needs NOT related to COVID = ‘YES’
 

4	Hospitalised, not requiring supplemental oxygen, requiring on-going COVID related care	
DAILY TREATMENT CRF (day 15):
 
 
• Any supplemental oxygen = NO
 
• Non-invasive respiratory support = NO
 
• Invasive respiratory support = NO
 
• Non-invasive ventilation = NO
 
• High-flow nasal cannula = NO
 
• ECMO = NO
 

5	Hospitalised, requiring supplemental oxygen	
DAILY TREATMENT CRF (day 15):
 
 
• Any supplemental oxygen = YES
 
• Non-invasive respiratory support = NO
 
• Invasive respiratory support = NO
 
• High-flow nasal cannula = NO
 
• ECMO = NO
 

6	Hospitalised, on non-invasive ventilation or high flow oxygen devices	
DAILY TREATMENT CRF (day 15):
 
 
• Non-invasive respiratory support = YES
 
OR
 
• High-flow nasal cannula = YES
 
 
AND
 
 
• Invasive respiratory support = NO
 
• ECMO = NO
 
 
OR
 
 
• FiO2 >0.4, or FiO2 >40%
 

		
OR
 
 
• O2 flow > 4 L/min
 

7	Hospitalised, on mechanical ventilation or ECMO	
DAILY TREATMENT CRF (day 15):
 
 
• Invasive respiratory support =YES
 
 
OR
 
 
• ECMO = YES
 

8	Death	
OUTCOME CRF (dated day 15 or less):
 
 
• Death= YES
 

NA	Unable to classify	If death before day 15, lost to follow-up prior to day 15, or due to incomplete CRF completion

\* If use of supplemental oxygen is unknown or missing, use either (1) DAILY CRF: recorded “Oxygen saturation” SpO2 lowest % is  $\geq 94\%$ ; or (2) DAILY CRF: recorded “Oxygen saturation” SpO2 lowest % is  $\geq 88\%$  plus: Admission CRF co-morbidities “Chronic pulmonary disease” is “Yes”.

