### 17.2.2.3. Time-to-death

We restrict this analysis to deaths within 28 days of baseline. Any patient alive at the end of the study period will be censored at 28 days. Any patient lost to follow-up prior to 28 days will be censored at their last known follow-up. This outcome will be analysed as a time-to-event using the methodology described in 17.2.2.1 above.

### 17.2.2.4. Clinical status at day 15

Clinical status is defined as an 8-point ordinal score with the following categories: (1) Not hospitalised, and not limited physically; (2) Not hospitalised, but limited physically and/or requiring supplementary oxygen; (3) Hospitalised but medically OK; (4) Hospitalised, not requiring supplementary oxygen, but needs on-going COVID related care; (5) Hospitalised and requiring supplementary oxygen; (6) Hospitalised and requiring non-invasive ventilation; (7) Hospitalised and requiring mechanical ventilation or ECMO; (8) Dead. See Appendix A1.1 below for a definition of how this outcome is derived. Where day 15 CRFs are unavailable, we will look at all available adjacent CRFs to estimate a

---

g We have used the same definition for this outcome as was used in the ACTT-1 trial.

most likely clinical status. In cases where there is ambiguity over likely clinical status, and independent statistical reviewer, blind to all but the clinical status CRF data, will adjudicate likely status. If it is not possible to estimate the outcome, the outcome will be treated as missing.

The outcome will be analysed using a proportional odds model with treatment arm and disease severity as covariates, and adjusting for key confounders: age, sex, and number of comorbidities at baseline. The treatment odds ratio estimated from the model will be presented along with a 95% CI and a p-value.

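### SAP Appendix Table 1 scores some inpatients as not hospitalised and lets one patient meet two rows (5 and 6; as printed, 6 and 7; also 3 and 4), so the day 15 ordinal score is wrong or not unique

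*SAP*

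**What the plan says.** Section 17.2.2.4 names eight categories for clinical status at day 15 and sends the reader to the appendix for the derivation, so Table 1 is the rule that will be programmed. The score is then analysed with a proportional odds model.

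- **Score 1.** The text has "1) Not hospitalised, and not limited physically", with no inpatient branch. The table's label is "Not hospitalised, and no limitations on activities", but its fields offer two routes. One is discharge alive with self-care no worse and no oxygen. The other is the hospitalisation field = yes together with "Medically fit for discharge" = yes.
- **Score 3.** The text has "3) Hospitalised but medically OK". The table's fields are hospitalisation = yes and "Ongoing health care needs NOT related to COVID" = yes.
- **Score 4.** The table's label speaks of continuing COVID care, but its fields ask only that six support items on the day 15 daily form are all no.
- **Score 5.** The label is "Hospitalised, requiring supplemental oxygen". Oxygen must be yes, and non-invasive support, invasive support, high-flow cannula and ECMO must be no. FiO2 and flow are not limited.
- **Score 6.** The text has "6) Hospitalised and requiring non-invasive ventilation". The table has "Hospitalised, on non-invasive ventilation or high flow oxygen devices", and after the device conditions (with invasive support and ECMO = no) it adds two further OR branches: FiO2 above 0.4, or O2 flow above 4 L/min.
- **Score 7.** Invasive support = yes or ECMO = yes.

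**The concern.** An ordinal outcome needs rows that are mutually exclusive, or a stated order in which they are tried. Table 1 has neither. One row also contradicts its own label, because an inpatient is filed under a not-hospitalised category with no check of function or oxygen.

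Two competent programmers could therefore derive different datasets from the same forms, and the odds ratio would depend on the order of their code. Section 9.2 notes that the cohort includes hospital-acquired cases and some patients in long-term institutional care, so inpatients who are fit to leave are foreseeable. Section 11 says the outcomes are defined so that they can be compared directly with the two cited trials, and a footnote ties this outcome to one of them. That purpose needs category boundaries that do not move with the programming.

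**Working it through.** The plan gives no figure to reproduce. The check is one of logic, using the row conditions in Table 1 and the category names in Section 17.2.2.4.

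**1. Score 1 against score 3** (inpatient, outcome form dated day 15 or less)

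| Fit for discharge | Non-COVID needs | Table 1 rows met | Text, taking fit for discharge as medically OK |
|---|---|---|---|
| yes | no | 1 | 3 |
| yes | yes | 1 and 3 | 3 |

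The first line is a contradiction: 3 − 1 = 2 categories. The second is a double assignment. It can occur only if the two form fields are not exclusive options, which the SAP does not show.

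**2. Rows 5 and 6.** Row 5 fixes oxygen = yes and the four advanced supports = no. Two indicators remain free, FiO2 > 0.4 and flow > 4 L/min, giving 2 × 2 = 4 field patterns. Row 6 is met if either is true, so 4 − 1 = 3 of the 4 patterns meet both rows. Example: oxygen at 6 L/min with no high-flow device or ventilation. Because invasive support and ECMO are already no in row 5, this holds however row 6 is bracketed.

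**3. Rows 6 and 7.** Take seven yes/no fields: oxygen, non-invasive support, invasive support, high-flow, ECMO, FiO2 > 0.4, flow > 4 L/min. Row 7 needs invasive support or ECMO, which is 3 of 4 combinations of those two; the other five fields are free: 3 × 2^5 = 96 patterns. The overlap with row 6 depends on its grouping:

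| Reading of row 6 | Condition that also meets row 6 | Patterns of 96 |
|---|---|---|
| Grouped as printed, FiO2 and flow stand alone | FiO2 or flow high | 96 × 3/4 = 72 |
| AND binds before OR | non-invasive support, or FiO2 or flow high | 96 × 7/8 = 84 |
| Invasive = no and ECMO = no govern every branch | none | 0 |

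Example: invasive ventilation with FiO2 0.6 meets rows 6 and 7 on the first two readings and row 7 alone on the third.

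**4. Rows 5 and 7.** No overlap. Row 5 requires invasive support = no and ECMO = no; row 7 requires one of them to be yes.

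**5. Rows 3 and 4.** Row 3 is read from the outcome form, row 4 from the day 15 daily form. Row 4's fields do not test for COVID-related care. An inpatient who meets row 3 and has a daily form showing no support meets row 4 as well.

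The counts in steps 2 and 3 are field patterns, not patient frequencies.

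**The case against.** The best defence of the score 1 branch is that it is a deliberate proxy: a patient fit for discharge would be at home but for a delay. Section 9.2 points the same way for time to recovery, where a patient still in hospital without COVID-related needs counts as recovered. But the ordinal scale has its own category for such inpatients, score 3, and neither the score 1 label nor the text announces an exception. Equating the form field with the text's wording is an inference, though the natural one.

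Section 17.2.2.4 also provides an independent statistical reviewer for ambiguous status. That sentence follows the rule for unavailable day 15 forms and sets no order between rows. It is partial mitigation; a complete form that meets two rows is a fault of definition, not an uncertain status.

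The text's score 6 can fairly be called a short name that the table elaborates. That answers the mention of high-flow devices, but not the overlap with row 5.

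Some stronger readings do not stand:

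- A reader might infer that scores 5, 6 and 7 all overlap. Rows 5 and 7 never do, and the 6/7 overlap disappears if the no-invasive, no-ECMO conditions were meant for the whole of row 6.
- A reader might count score 2 as a further fault, because its AND/OR list has no brackets. Its label and the text already fix the meaning: discharged, and either limited or on oxygen.
- A reader might put a number on the misplaced patients or infer a biased treatment effect. The SAP gives no frequency for any of these states, and the same rule applies to both groups, so neither the size nor the direction follows.
- A reader might infer misclassification against the cited trial's scale. That scale is not reproduced in the SAP, so this cannot be checked.

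**Conclusion.** The point holds for two errors in the operative table. First, the inpatient branch of score 1 contradicts its own label and, with fit for discharge read as medically OK, the text's score 3; each patient affected moves two categories, to the best score. Second, rows 5 and 6 are not exclusive on any reading, and rows 6 and 7 are not exclusive as printed. Rows 3 and 4 also overlap, which matters for the remedy.

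The consequence is a score that is wrong or not unique for some patients in one secondary analysis. The effect on its odds ratio cannot be quantified from the SAP. The primary outcome, 14-day mortality, is unaffected. The correction should be made, but it does not threaten the study's main conclusion.

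**What to change.** 1. Move the inpatient fit-for-discharge branch from score 1 to score 3. The row 3 label excludes supplemental oxygen but its fields do not test for it, so state that condition too.
2. Settle rows 5 and 6 one way. Either add FiO2 ≤ 0.4 and flow ≤ 4 L/min to row 5 and state the FiO2/flow criterion under score 6 in Section 17.2.2.4, or delete that criterion from row 6.
3. Apply invasive support = no and ECMO = no to every branch of row 6.
4. Make row 4 exclude patients who meet row 3.

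A bare rule of assigning the worst score met should not be used in place of these edits. With rows 3 and 4 overlapping, it would push medically OK inpatients with a day 15 daily form showing no support from 3 to 4 and largely empty score 3. It is safe only once those two rows are mutually exclusive.

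The cost is an edit to the table and the matching text, the derivation code, and an entry in Change Control, which Section 7 already requires for changes. No new data are needed. It should be done before the score is derived.

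### Appendix Table 1 leaves the Non-invasive ventilation item out of the rules for scores 5 and 6, so a patient whose NIV is recorded only there can score 5, fit no row, or meet both rows

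*SAP*

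**What the plan says.** Section 17.2.2.4 of the SAP sets out an eight-category ordinal scale for clinical status at day 15. It describes one category as "6) Hospitalised and requiring non-invasive ventilation" and sends the reader to the Appendix for the derivation. Table 1 there maps each score to named ISARIC fields. For patients still in hospital and needing COVID-related care or respiratory support, the relevant rows use the day-15 Daily Treatment CRF:

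- **Score 4.** Six items must all be NO. Non-invasive respiratory support is one, and "Non-invasive ventilation = NO" is listed separately.
- **Score 5**, labelled "Hospitalised, requiring supplemental oxygen". It needs "Any supplemental oxygen = YES", with four items at NO: non-invasive respiratory support, invasive respiratory support, high-flow nasal cannula and ECMO. The Non-invasive ventilation item is not mentioned.
- **Score 6**, labelled "Hospitalised, on non-invasive ventilation or high flow oxygen devices". The device route is "Non-invasive respiratory support = YES" or high-flow nasal cannula YES, with invasive support and ECMO both NO. Two alternatives are joined by OR: "FiO2 >0.4, or FiO2 >40" per cent, and "O2 flow > 4 L/min". The Non-invasive ventilation item is again not mentioned.
- **Score 7.** Invasive respiratory support or ECMO is YES.

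A final row, for patients who cannot be classified, gives as reasons death or loss to follow-up before day 15 and incomplete CRFs. The SAP does not say how the two non-invasive items relate to each other.

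**The concern.** The row label and the body text agree that NIV belongs in category 6, but the derivation rule does not use the item that carries that name. Score 4 treats it as a field distinct from non-invasive respiratory support, since it requires both to be NO. A YES in that field therefore keeps a patient out of score 4 but does not take the patient into score 6 or keep the patient out of score 5.

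At stake is the accuracy of the category 5 and 6 counts in secondary outcome 4. Section 9.2 takes that outcome from ACTT-1, and Section 11 says outcomes are defined to allow direct comparison with that trial. A programmer who follows Table 1 literally would count some patients on NIV as needing oxygen only, and would have no rule for others.

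**Working it through.** The SAP states no figure on this point, so the check is to apply the rules for scores 4 to 7 literally.

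**Set-up.** Take a day-15 inpatient with Non-invasive ventilation = YES, invasive support = NO and ECMO = NO. Four things can still vary: supplemental oxygen, non-invasive respiratory support (NIRS), high-flow nasal cannula (HFNC), and whether FiO2 is above 0.4 or flow above 4 L/min (high). That gives 2 × 2 × 2 × 2 = 16 combinations.

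**Step 1: NIRS or HFNC is YES.** There are 3 such pairs (NIRS only, HFNC only, both), each with 2 × 2 = 4 settings of oxygen and FiO2/flow, so 12 combinations. Score 6 is met through its device route. Score 5 is blocked because it needs both items at NO. All 12 score 6 and nothing else.

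**Step 2: NIRS and HFNC are both NO.** Four combinations remain:

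| Oxygen | FiO2 or flow high | Rows met as written |
|---|---|---|
| YES | no | 5 only |
| YES | yes | 5 and 6 |
| NO | no | none |
| NO | yes | 6 only |

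In the third line score 4 fails precisely because Non-invasive ventilation is YES, score 5 fails because oxygen is NO, score 6 has no open route, and score 7 does not apply. If the CRF is complete, the reasons listed in the unable-to-classify row do not cover this patient either.

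**Total as written.** 12 + 1 = 13 combinations score 6 only, 1 scores 5 only, 1 meets both 5 and 6, and 1 meets no row. These are counts of logical combinations, not patient frequencies.

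**Step 3: repeat with the item added.** With Non-invasive ventilation = NO required for score 5, and = YES accepted as a device route into score 6, all 16 combinations score 6 and only 6.

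**Step 4: likely effect on the odds ratio.** The SAP gives no category distribution, so this is illustration only. Assume controls fall 40/15/5/6/10/7/5/12% across scores 1 to 8, and a common odds ratio of 0.750 for a worse category. Fit a proportional odds model to the expected counts after taking 25%, 50% or 100% of category 6 in each group and either moving it to category 5 or removing it as missing. The fitted odds ratio lies between 0.750 and 0.751 throughout with equal group sizes. The counts do change: at 50%, 0.5 × 7% = 3.5% of controls are scored 5 or lost, which halves category 6.

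A deliberately extreme case is a treatment effect confined to NIV: 7% falls to 3.5%, those patients move to score 5, and every NIV patient is read as 5. The odds ratio then goes from 0.98 to 1.00, which follows by construction because categories 5 and 6 have been merged.

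**The case against.** The strongest objection is that the CRF is not shown, and non-invasive respiratory support may be the operative item, answered YES whenever NIV is in use. The table has a parallel: score 7 is labelled by mechanical ventilation and derived from invasive respiratory support. On that reading the extra line under score 4 is redundant and nobody is misclassified. This stands as a limit on the harm that can be shown. It does not remove the gap, because the SAP never states the relation and score 4 tests the two items separately.

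A second objection is that Section 17.2.2.4 provides for adjacent CRFs and a blinded independent statistical reviewer. Adjudication may catch the patient who fits no row or meets two. The use of adjacent CRFs is for cases where day-15 forms are unavailable. Neither helps a patient who cleanly meets the rule for score 5, because nothing about that record looks ambiguous.

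Three stronger readings are tempting, and the document does not support them:

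- A reader might infer that every patient with the Non-invasive ventilation item at YES is mis-scored. That is wrong for 13 of the 16 combinations.
- A reader might infer that the patient with no row is set to missing by rule. The unable-to-classify row does not name a complete form that matches nothing.
- A reader might infer that the gap carries over to time to first ventilation and any use of NIV (Sections 17.2.2.6 and 17.2.2.7). Neither section refers to Table 1 or adopts its rule for score 6, so that would be conjecture.

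**Conclusion.** The derivation is wrong as written for an identifiable set of patients: those whose NIV is recorded only in the Non-invasive ventilation item, with NIRS, HFNC, invasive support and ECMO all NO. Without a high FiO2 or flow they score 5 if on supplemental oxygen and fit no row if not. With oxygen and a high FiO2 or flow they meet two rows and no precedence is given.

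Severity is low. Only secondary outcome 4 is affected, mainly the split between categories 5 and 6; the primary outcome is untouched. How often the two items disagree cannot be learned from the SAP and may be close to never. Under the assumed distribution above, the common odds ratio hardly moves, so a material bias in the treatment effect should not be claimed. The case for correcting it is that the rule should match its own label and Section 17.2.2.4, and that the correction does no harm if the items never disagree.

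**What to change.** In Appendix Table 1:

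1. Score 5: add the condition Non-invasive ventilation = NO.
2. Score 6: extend the first condition to NIRS = YES, or Non-invasive ventilation = YES, or HFNC = YES. Leave the rest of the row as it is.
3. State that score 6 takes precedence over score 5 when both are met. This is still needed after steps 1 and 2, because a patient with all device items at NO, on oxygen with a high FiO2 or flow, also meets both rows.

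If the CRF guarantees that NIRS is YES whenever NIV is used, a sentence saying so would settle the item question, but the precedence rule would still be required.

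The cost is a few words in the SAP, an entry in its change control table and a small edit to the derivation code. No new data are needed.
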